14.6. Appendix 6: Values of Potential Clinical Importance

14.6.1. Laboratory Values of Potential Clinical Concern

Haematology				
Laboratory Parameter	Units	Age Category	Clinical Concern Range	
			Low Flag (< x)	High Flag (>x)
Hematocrit	Ratio of 1	12+	0.201	0.599
Haemoglobin	G/L	12+	71	199
Platelet Count	GI/L	1+	31	1499
While Blood Cell Count (WBC)	GI/L	12+	1.1	

Clinical Chemistry				
Laboratory Parameter	Units	Age Category	Clinical Concern Range	
			Low Flag (< x)	High Flag (>x)
ALT	U/L	3-12		>143 (and Total Bilirubin >43)
	U/L	13+		>239 (and Total Bilirubin >43)
Calcium	mmol/L	3+	1.50	3.24
Glucose	mmol/L	1+	2.2	27.8
Phosphorus, Inorg	mmol/L	3+	0.32	
Potassium	mmol/L	3+	2.8	6.5
Sodium	mmol/L	0+	120	160

Possible Hy's Law Cases				
Laboratory Parameter	Units	Category	Clinical Concern Range	
ALT, Bilirubin			ALT \geq 3xULN and Bilirubin \geq 2xULN (>35% direct)	
ALT, INR			ALT \geq 3xULN and INR > 1.5	

NOTES:

- ULN = Upper Limit of Normal.

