12.4. Appendix 4: Liver Safety Required Actions and Follow up Assessments

12.4.1. Liver chemistry stopping criteria and required follow up assessments

Liver Chemistry Stopping Criteria - Liver Stopping Event	
ALT-absolute	ALT \geq 8xULN
ALT Increase	ALT \geq 5xULN but <8xULN persists for \geq 2 weeks ALT \geq 3xULN but <5xULN persists for \geq 4 weeks
Bilirubin^{1,2}	ALT \geq 3xULN and bilirubin \geq 2xULN (>35% direct bilirubin)
INR²	ALT \geq 3xULN and INR>1.5, if INR measured
Cannot Monitor	ALT \geq 5xULN but <8xULN and cannot be monitored weekly for \geq 2 weeks ALT \geq 3xULN but <5xULN and cannot be monitored weekly for \geq 4 weeks
Symptomatic³	ALT \geq 3xULN associated with symptoms (new or worsening) believed to be related to liver injury or hypersensitivity
Required Actions and Follow up Assessments following ANY Liver Stopping Event	
Actions	Follow Up Assessments

 Immediately discontinue study treatment Report the event to GSK within 24 hours Complete the liver event CRF and complete an SAE data collection tool if the event also meets the criteria for an SAE² Perform liver event follow up assessments Monitor the subject until liver chemistries resolve, stabilize, or return to within baseline (see MONITORING below) Do not restart/rechallenge subject with study treatment. Permanently discontinue study treatment and may continue subject in the study for any protocol specified follow up assessments 	
 Viral hepatitis serology⁴ Only in those with underlying chronic hepatitis B at study entry (identified by positive hepatitis B surface antigen) quantitative hepatitis B DNA and hepatitis delta antibody⁵. Blood sample for pharmacokinetic (PK) analysis, obtained within 4 weeks after last dose⁶ Serum creatine phosphokinase (CPK) and lactate dehydrogenase (LDH). Fractionate bilirubin, if total bilirubin \geq 2xULN Obtain complete blood count with differential to assess eosinophilia. Note: The mechanism of action of mepolizumab leads to lowering of eosinophils.

Liver Chemistry Stopping Criteria - Liver Stopping Event	

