11.33	All Subjects	TAB_S1	Summary Profile of On-Treatment Adverse Events Categorised as Serious Ischemic Events		SAC
11.34	All Subjects	AE1	Summary of On-Treatment Adverse Events Categorised as Malignancies		SAC
11.35	All Subjects	TAB_S1	Summary Profile of On-Treatment Adverse Events Categorised as Malignancies		SAC
11.36	All Subjects	AE1	Summary of On-Treatment Adverse Events Categorised as Opportunistic Infections		SAC
11.37	All Subjects	TAB_S1	Summary Profile of On-Treatment Adverse Events Categorised as Opportunistic Infections		SAC
Laboratory - Haematology					
11.38	All Subjects	LB1	Summary of Haematology Changes from Baseline by Visit	Include baseline values	SAC
11.39	All Subjects	LB3	Summary of Haematology Shifts from Baseline Relative to Normal Range by Visit		SAC

CONFIDENTIAL

205667

No.	Population	IDSL / TST ID / Example Shell	Title	Programming Notes	Deliverable [Priority]
Safety : Tables					
11.40	All Subjects	LB3	Summary of Haematology Shifts from Baseline Relative to PCI Criteria by Visit		SAC
Laboratory – Clinical Chemistry					
11.41	All Subjects	LB1	Summary of Clinical Chemistry Changes from Baseline by Visit	Include baseline values	SAC
11.42	All Subjects	LB3	Summary of Clinical Chemistry Shifts from Baseline Relative to Normal Range by Visit		SAC
11.43	All Subjects	LB3	Summary of Clinical Chemistry Shifts from Baseline Relative to PCI Criteria by Visit		SAC
ECG					
11.43	All Subjects	EG1	Summary of ECG Findings by Visit		SAC
11.45	All Subjects	EG2	Summary of ECG Values by Visit		SAC
11.46	All Subjects	EG2	Summary of Change from Baseline in ECG Values by Visit	Include baseline values	SAC
Vital Signs					
11.47	All Subjects	VS1	Summary of Vital Signs by Visit		SAC
11.48	All Subjects	VS1	Summary of Change from Baseline in Vital Signs by Visit	Include baseline values	SAC
Injection Pain Assessments					
11.49	All Subjects	TAB_S3	Summary of Injection Pain – VAS Scores (mm)	By Visit and time point post-injection (injection, 1 hr post, 24 hrs post)	SAC
11.50	All Subjects	TAB_S4	Summary of Injection Pain – Categorical Pain Assessment	By Visit and time point post-injection (injection, 1 hr post, 24 hrs post)	SAC

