31	All Subjects	AE8	Listing of Adverse Events Categorised as Opportunistic Infections	Add phase: Pre-treatment, on-treatment, post-treatment (see Section 14.2.1.1).	SAC
Laboratory					
32	All Subjects	LB5	Listing of Haematology Data for Subjects with Abnormalities of Potential Clinical Concern		SAC
33	All Subjects	LB5	Listing of Chemistry Data for Subjects with Abnormalities of Potential Clinical Concern		SAC

ICH and Other Listings					
No.	Population	IDSL / TST ID / Example Shell	Title	Programming Notes	Deliverable [Priority]
Injection Pain					
34	All Subjects	LIST_S1	Listing of Injection Pain Assessment		SAC

ICH and Other Listings					
No.	Population	IDSL / TST ID / Example Shell	Title	Programming Notes	Deliverable [Priority]
Immunogenicity					
35	All Subjects	IMM2	Listing of Immunogenicity Data for Subjects with at Least One Positive Screening Binding Assay	Include columns for Screening Binding Assay, Confirmation Binding Assay, Confirmation Binding Assay Titre, Transient/Persistent, Neutralizing Antibody Assay	SAC

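### Isolated ALT elevations meeting four of the protocol's six liver stopping categories are not identified by the SAP's clinical-concern criteria, and no liver-event display is listed

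*SAP*

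**What the plan says.** **Criteria.** SAP 14.6.1 sets the ALT high flag in U/L. At age 13 and over it is ">239 (and Total Bilirubin >43"; at ages 3 to 12, which in this trial means 12-year-olds, it is ">143 (and Total Bilirubin >43". Both are joint conditions. The same section adds two Hy's Law rows: ALT at least 3xULN with bilirubin at least 2xULN and more than 35% direct, and ALT at least 3xULN with INR above 1.5.

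**Displays that use them.** These are SAP 14.8.6, "Summary of Clinical Chemistry Shifts from Baseline Relative to PCI Criteria by Visit" (Table 11.43, a number also given to the ECG findings table), and SAP 14.8.8, "Listing of Chemistry Data for Subjects with Abnormalities of Potential Clinical Concern" (Listing 33).

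**Protocol.** Section 12.4.1, under "Liver Chemistry Stopping Criteria - Liver Stopping Event", has six categories: ALT absolute, ALT increase, bilirubin, INR, cannot monitor, symptomatic. Its footnotes say that INR need not be measured. The actions include completing a liver event CRF. Section 12.4.2 covers ALT from 3xULN to below 8xULN with treatment continued under weekly monitoring.

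**The concern.** Clinically significant change in chemistry parameters is a named safety endpoint (Protocol 3, SAP 2.2). The concern-range displays are where a reader would look for large laboratory abnormalities in individual subjects. If a subject meets a stopping criterion on ALT alone and those displays show no ALT abnormality, the report reads as cleaner than the data. Subjects enter with ALT at most 2xULN (Protocol 5.3), so a later value of 3xULN or more would be a new rise and worth showing.

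**Working it through.** No design figure is involved, so this is a check of logic across the two documents.

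**Step 1: the flag as a rule.** I assume, in the plan's favour, that the Hy's Law rows feed Table 11.43 and Listing 33. A subject aged 13 or over is then flagged for liver chemistry if any of these holds:
- A: ALT > 239 and total bilirubin > 43
- B: ALT ≥ 3xULN and bilirubin ≥ 2xULN and direct fraction > 35%
- C: ALT ≥ 3xULN and INR > 1.5

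If bilirubin is not raised, and INR is unmeasured or at most 1.5, then A, B and C are all false whatever the ALT. This needs no assumed ULN. At age 12, A uses 143 and the result is the same.

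**Step 2: the six stopping categories, with bilirubin and INR not raised unless the category requires it.**

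| Protocol 12.4.1 category | Flagged under SAP 14.6.1? |
|---|---|
| ALT ≥ 8xULN | No |
| ALT 5x to <8xULN for ≥2 weeks, or 3x to <5xULN for ≥4 weeks | No |
| Same ALT bands, weekly monitoring not possible | No |
| ALT ≥ 3xULN with symptoms | No |
| ALT ≥ 3xULN with bilirubin ≥ 2xULN, >35% direct | Yes (B) |
| ALT ≥ 3xULN with INR > 1.5 | Yes (C), if INR was measured |

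**Step 3: illustration.** The documents give no ULNs. Assume an ALT ULN of 30 to 60 U/L and a bilirubin ULN of 21, in the units of the SAP's threshold of 43.
- ALT 8xULN = 240 to 480, bilirubin 0.5 × 21 = 10.5: no flag.
- ALT 20xULN = 600 to 1,200, bilirubin 10.5: no flag.
- ALT 8xULN, bilirubin 1.9 × 21 = 39.9: no flag.
- ALT 3xULN = 90 to 180, bilirubin 2 × 21 = 42, >35% direct: B.
- ALT 3xULN, INR 1.6: C.
- ALT 8xULN, bilirubin 2.5 × 21 = 52.5, >35% direct: A and B.

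**Step 4: where else could an isolated rise appear?**
- Table 11.42 (shifts against the normal range) counts it as High, but 1.1xULN and 10xULN fall in the same category.
- Table 11.41 (changes from baseline) is a group summary. It does not identify the subject or the multiple of ULN.
- Table 6.4 and Listing 3 (treatment discontinuation), and Table 6.5 and Listing 4 (study withdrawal), show a stop made while doses remain. Doses are at Weeks 0, 4 and 8, but chemistry is also drawn at Week 12. A value first seen then has no treatment left to discontinue, and a subject who completes that visit is a completer (Protocol 5.6). Rises under Protocol 12.4.2 continue treatment.
- AE displays show it only if the investigator judges the value clinically significant (Protocol 12.6.1). The liver-specific SAE criterion needs bilirubin or INR (Protocol 12.6.2).
- Repeat tests required by Appendix 4 of the protocol are unscheduled. SAP 14.3.2 and 14.4.1 keep unscheduled values out of summary tables when the nominal visit already has data, and send them to listings. The only chemistry listing is Listing 33, which such a subject enters only through some other flagged value. A peak on a repeat test can therefore appear in no chemistry display.

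**Step 5: would deleting the bilirubin condition be enough?** 239 / 8 = 29.9, so ALT > 239 alone would catch every value at or above 8xULN for a ULN of 30 or more. At a ULN of 40, however, 3xULN = 120 and 5xULN = 200, both below 239. A fixed cut would miss part of the lower bands.

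**The case against.** The best defence is that these events are not lost. A liver stop requires immediate discontinuation and a report within 24 hours, and it is a withdrawal criterion (Protocol 5.5.1). The reason then reaches the discontinuation and withdrawal displays whether or not an AE is recorded. This stands for stops made while doses remain. It does not cover a value first seen at Week 12 or monitoring-level rises on continued treatment.

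Second, the protocol never says that concern ranges must mirror the stopping rules, and a high-specificity reporting flag is a legitimate choice. That is right: the documents do not contradict each other. But the SAP gives no reason for the choice, and its list includes inorganic phosphorus, which is not among the chemistry tests in Protocol Table 3. That suggests a standard list that was not fitted to this protocol.

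Third, few events are likely: about 55 subjects, three doses, entry ALT at most 2xULN. This limits the practical weight, although the documents give no event rate.

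A reader might infer two stronger claims, and neither is supported. One is that ALT values meeting the stopping rule are never flagged in the safety displays. The Hy's Law rows match the bilirubin and INR categories, and Tables 11.41 and 11.42 do not use the flag at all. The other is that the numeric ALT row adds nothing to the Hy's Law rows. That rests on assumed ULNs and ignores that the Hy's Law bilirubin row needs more than 35% direct bilirubin while the numeric row does not.

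**Conclusion.** The point holds as a reporting gap. With bilirubin and INR not raised, or INR not measured, four of the six protocol stopping categories produce no concern flag at any ALT value. This follows from the joint condition and does not depend on the assumed ULNs, which serve only the illustration. The event may still surface elsewhere, but without its size relative to ULN, and not reliably at Week 12 or on repeat tests. Liver monitoring and stopping run from the protocol and do not use this flag, so subject protection during the study is unaffected, as are the primary and secondary endpoints. It is worth correcting because the stated rule can make a named safety endpoint look clean when it is not.

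**What to change.** Reconcile SAP 14.6.1 with Appendix 4 of the protocol for reporting purposes only; no clinical rule changes.

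- Add flags for ALT alone at the protocol's own multiples (at least 3x, 5x and 8xULN) and use them in the chemistry Table 11.43 and in Listing 33.
- Label them as ALT elevations, not stopping events. The 3x and 5x stopping rules also need persistence, symptoms or inability to monitor, and such subjects may properly be continuing treatment.
- Keep the existing ALT/bilirubin and ALT/INR rows.
- Apply the flags to unscheduled values too, and have Listing 33 show all scheduled and unscheduled liver chemistries for any flagged subject. Table 11.43 will still omit repeat values that the visit rule excludes, so the listing has to carry them.
- State in Appendix 8 of the SAP where data from the liver event CRF, if any, will be reported.

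The cost is an SAP edit, minor programming for three tiers in one table and one listing, and a few more listing rows. All the data are already collected.

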14.7. Appendix 7: Abbreviations & Trade Marks

14.7.1. Abbreviations

Abbreviation	Description
ADA	Anti-drug Antibody
ADaM	Analysis Data Model
AE	Adverse Event
A&R	Analysis and Reporting
BLQ	Below the Limit of Quantification
CDISC	Clinical Data Interchange Standards Consortium
CI	Confidence Interval
CPMS	Clinical Pharmacology Modelling & Simulation
CS	Clinical Statistics
CSR	Clinical Study Report
CTR	Clinical Trial Register
Ctrough	Concentration at the end of the dosing interval
DOB	Date of Birth
DP	Decimal Places
eCRF	Electronic Case Record Form
IA	Interim Analysis
ICH	International Conference on Harmonisation
IDMC	Independent Data Monitoring Committee
IDSL	Integrated Data Standards Library
IMMS	International Modules Management System
IP	Investigational Product
GUI	Guidance
GSK	GlaxoSmithKline
PCI	Potential Clinical Importance
PD	Pharmacodynamic
PDMP	Protocol Deviation Management Plan
PK	Pharmacokinetic
QC	Quality Control
QTcF	Frederica's QT Interval Corrected for Heart Rate
QTcB	Bazett's QT Interval Corrected for Heart Rate
RAP	Reporting & Analysis Plan
SAC	Statistical Analysis Complete
SDTM	Study Data Tabulation Model
SOP	Standard Operation Procedure
TA	Therapeutic Area
TFL	Tables, Figures & Listings
ULN	Upper Limit of Normal
VAS	Visual Analogue Scale

14.7.2. Trademarks

Trademarks of the GlaxoSmithKline Group of Companies
NONE

Trademarks not owned by the GlaxoSmithKline Group of Companies
SAS

14.8. Appendix 8: List of Data Displays

14.8.1. Study Population Tables

Study Population - Tables					
No.	Population	IDSL / TST ID / Example Shell	Title	Programming Notes	Deliverable [Priority]
6.1	ASE	TAB_POP1	Summary of Study Populations		SAC
6.2	ASE	ES6	Summary of Screen Failures	Include footnote "Note: Inclusion/exclusion criteria include protocol defined continuation criteria."	SAC
6.3	ASE	NS1	Summary of Number of Subjects by Country and Site	"Not Treated" column should be added to include subjects who did not receive treatment.	SAC
6.4	All Subjects	SD1	Summary of IP Discontinuation		SAC
6.5	All Subjects	ES1	Summary of Subject Disposition		SAC
6.6	All Subjects	DV1	Summary of Important Protocol Deviations		SAC
6.7	All Subjects	EX1	Summary of Exposure to Study Treatment (months)	Categories 1, 2, 3 months Summary statistics for duration of exposure (months)	SAC
6.8	All Subjects	TAB_EX1	Summary of Injection Site by Visit		SAC
6.9	All Subjects	DM1	Summary of Demographic Characteristics		SAC
6.10	All Subjects	DM5	Summary of Race and Racial Combinations		SAC
6.11	ASE	DM11	Summary of Age Ranges	"Not Treated" column should be added to include subjects who did not receive treatment.	SAC
6.12	All Subjects	TAB_POP2	Summary of Disease Duration		SAC
6.13	All Subjects	TAB_POP3	Summary of Prior Experience with Self-Injection of Medication		SAC
6.14	All Subjects	TAB_POP4	Summary of Baseline Mepolizumab Use		SAC
6.15	All Subjects	MH1	Summary of Past Medical Conditions		SAC
6.16	All Subjects	MH1	Summary of Current Medical Conditions		SAC
6.17	All Subjects	FH1	Summary of Family History of Cardiovascular Risk Factors		SAC

Study Population - Tables					
No.	Population	IDSL / TST ID / Example Shell	Title	Programming Notes	Deliverable [Priority]
6.18	All Subjects	SU1	Summary of Smoking History	Smoking status (current/former/never) only	SAC

14.8.2. Evaluation of Safety Syringe

No.	Population	IDSL / TST ID / Example Shell	Title	Programming Notes	Deliverable [Priority]
Evaluation of Safety Syringe - Tables					
7.1	All Subjects	TAB_INJ1	Summary of the Proportion of Subjects Successfully Able to Self-Administer Injection by Visit		SAC
7.2	All Subjects	TAB_INJ2	Summary of Investigator Evaluation of User/Device Errors by Visit		SAC
7.3	All Subjects	TAB_INJ3	Summary of Observer Checklist for In-Clinic Injections		SAC
7.4	All Subjects	TAB_INJ4	Summary of Subject Completed Checklist for At-Home Injection at Week 4		SAC
7.5	All Subjects	TAB_INJ5	Summary of Device Usability/Functionality Questionnaire		SAC

14.8.3. Pharmacokinetic Analyses

No.	Population	IDSL / TST ID / Example Shell	Title	Programming Notes	Deliverable [Priority]
PK Concentration: Figures					
8.1	PK	PK16a	Individual Plasma Mepolizumab Concentration-Time Plots (Linear and Semi-Log) by Subject	Subject number and baseline mepolizumab use as by-line. Indicate the injection site used for each dose using different plotting characters.	SAC
8.2	PK	PK26	Individual Plasma Mepolizumab Concentration-Time Plots (Linear and Semi-Log) by Baseline Mepolizumab Use	Baseline mepolizumab use as a by-line. All subjects in the same baseline mepolizumab group on the same graph ("spaghetti" plot).	SAC
8.3	PK	PK26	Individual Plasma Mepolizumab Concentration-Time Plots (Linear and Semi-Log) by Baseline Mepolizumab Use and Injection Site – Subjects Using the Same Injection Site Throughout the Study	Baseline mepolizumab use and injection site as a by-line. All subjects in the same baseline mepolizumab group and injection site on the same graph ("spaghetti" plot). Include only the subset of subjects using the same injection site for all doses of study treatment.	SAC
8.4	PK	PK17	Mean Plasma Mepolizumab Concentration-Time Plots by Baseline Mepolizumab Use (Linear and Semi-Log)		SAC
8.5	PK	PK18	Median Plasma Mepolizumab Concentration-Time Plots by Baseline Mepolizumab Use (Linear and Semi-Log)		SAC
8.6	PK	PK17	Mean Plasma Mepolizumab Concentration-Time Plots by Baseline Mepolizumab Use and Injection Site (Linear and Semi-Log) – Subjects Using the Same Injection Site Throughout the Study	Include only the subset of subjects using the same injection site for all doses of study treatment.	SAC

CONFIDENTIAL

205667

No.	Population	IDSL / TST ID / Example Shell	Title	Programming Notes	Deliverable [Priority]
8.7	PK	PK18	Median Plasma Mepolizumab Concentration-Time Plots by Baseline Mepolizumab Use and Injection Site (Linear and Semi-Log) – Subjects Using the Same Injection Site Throughout the Study	Include only the subset of subjects using the same injection site for all doses of study treatment.	SAC
Pharmacokinetic – Tables					
8.1	PK	PK01	Summary of Plasma Mepolizumab Concentration-Time Data		SAC
8.2	PK	PK01	Summary of Plasma Mepolizumab Concentration-Time Data by Baseline Mepolizumab Use		SAC
8.3	PK	PK01	Summary of Plasma Mepolizumab Concentration-Time Data by Baseline Mepolizumab Use and Injection Site – Subjects Using the Same Injection Site Throughout the Study	Include only the subset of subjects using the same injection site for all doses of study treatment.	SAC

14.8.4. Pharmacodynamic Analyses

No.	Population	IDSL / TST ID / Example Shell	Title	Programming Notes	Deliverable [Priority]
Pharmacodynamic – Figures					
9.1	PD	FIG_PD1	Geometric Mean (95% CI) Absolute Blood Eosinophils by Visit and Baseline Mepolizumab Use		SAC
9.2	PD	FIG_PD1	Geometric Mean (95% CI) Absolute Blood Eosinophils by Visit, Baseline Mepolizumab Use and Injection Site – Subjects Using the Same Injection Site Throughout the Study	Baseline mepolizumab use as by-line. Separate lines on graph corresponding to injection sites. Include only the subset of subjects using the same injection site for all doses of study treatment.	SAC
9.3	PD	FIG_PD1	Geometric Mean (95% CI) Ratio to Baseline Blood Eosinophils by Visit and Baseline Mepolizumab Use		SAC
9.4	PD	FIG_PD1	Geometric Mean (95% CI) Ratio to Baseline Blood Eosinophils by Visit, Baseline Mepolizumab Use and Injection Site – Subjects Using the Same Injection Site Throughout the Study	Baseline mepolizumab use as by-line. Separate lines on graph corresponding to injection sites. Include only the subset of subjects using the same injection site for all doses of study treatment.	SAC
Pharmacodynamic – Tables					
9.1	PD	TAB_PD1	Summary of Blood Eosinophils (GI/L) by Visit		SAC
9.2	PD	TAB_PD2	Summary of Ratio to Baseline Blood Eosinophils by Visit		SAC
9.3	PD	TAB_PD3	Summary of Blood Eosinophils by Visit and Baseline Mepolizumab Use		SAC
9.4	PD	TAB_PD4	Summary of Ratio to Baseline Blood Eosinophils by Visit and Baseline Mepolizumab Use		SAC

No.	Population	IDSL / TST ID / Example Shell	Title	Programming Notes	Deliverable [Priority]
9.5	PD	TAB_PD3	Summary of Blood Eosinophils by Visit, Baseline Mepolizumab Use and Injection Site– Subjects Using the Same Injection Site Throughout the Study	Add baseline mepolizumab use to by line, and include injection site in first column. Include only the subset of subjects using the same injection site for all doses of study treatment.	SAC
9.6	PD	TAB_PD4	Summary of Ratio to Baseline Blood Eosinophils by Visit, Baseline Mepolizumab Use and Injection Site– Subjects Using the Same Injection Site Throughout the Study	Add baseline mepolizumab use to by line, and include injection site in first column. Include only the subset of subjects using the same injection site for all doses of study treatment.	SAC

14.8.5. Exacerbations

No.	Population	IDSL / TST ID / Example Shell	Title	Programming Notes	Deliverable [Priority]
Exacerbations : Tables					
10.1	All Subjects	TAB_EX1	Summary of Number of Subjects with at Least One On-Treatment Exacerbation		SAC

14.8.6. Safety Analyses

CONFIDENTIAL

205667

No.	Population	IDSL / TST ID / Example Shell	Title	Programming Notes	Deliverable [Priority]
Safety : Tables					
Adverse Events					
11.1	All Subjects	AE1	Summary of All On-Treatment Adverse Events by System Organ Class and Preferred Term		SAC
11.2	All Subjects	AE1	Summary of All Post-Treatment Adverse Events by System Organ Class and Preferred Term		SAC
11.3	All Subjects	AE3	Summary of Common (>=3% Incidence) On-Treatment Adverse Events by Overall Frequency		SAC
11.4	All Subjects	AE15	Summary of Common (>=3% Incidence) On-Treatment Adverse Events by Preferred Term (Number of Subjects and Occurrences)		SAC
11.5	All Subjects	AE5A	Summary of All On-Treatment Adverse Events by Maximum Intensity by System Organ Class and Preferred Term		SAC
11.6	All Subjects	AE1	Summary of All Drug-Related Adverse Events by System Organ Class and Preferred Term		SAC
11.7	All Subjects	AE5A	Summary of All Drug-Related Adverse Events by Maximum Intensity by System Organ Class and Preferred Term		SAC
11.8	All Subjects	AE1	Summary of On-Treatment Adverse Events by Week 12 Binding Antibody Result	Add in row with n in each binding antibody result category. See Section 12.	SAC
11.9	All Subjects	AE3	Summary of All Adverse Events Leading to Permanent Discontinuation from Study Treatment and/or Withdrawal from the Study by Overall Frequency		SAC

CONFIDENTIAL

205667

No.	Population	IDSL / TST ID / Example Shell	Title	Programming Notes	Deliverable [Priority]
Safety : Tables					
11.10	All Subjects	AE1	Summary of Adverse Events Reported on the Day of Dosing by System Organ Class and Preferred Term		SAC
11.11	All Subjects	AE7	Listing of Subject Numbers for Individual On-Treatment Adverse Events		SAC
11.12	All Subjects	AE2	Listing of Relationship of Adverse Event, System Organ Classes, Preferred Terms and Verbatim Text		SAC
Serious Adverse Events					
11.13	All Subjects	AE3	Summary of Fatal Serious Adverse Events by Overall Frequency		SAC
11.14	All Subjects	AE3	Summary of Drug-Related Fatal Serious Adverse Events by Overall Frequency		SAC
11.15	All Subjects	AE1	Summary of All On-Treatment Serious Adverse Events by System Organ Class and Preferred Term		SAC
11.16	All Subjects	AE16	Summary of All On-Treatment Serious Adverse Events by System Organ Class and Preferred Term (Number of Subjects and Occurrences)		SAC
11.17	All Subjects	AE1	Summary of All Post-Treatment Serious Adverse Events by System Organ Class and Preferred Term		SAC
11.18	All Subjects	AE1	Summary of All Pre-Treatment Serious Adverse Events by System Organ Class and Preferred Term		SAC
11.19	All Subjects	AE1	Summary of All Drug-Related Serious Adverse Events by System Organ Class and Preferred Term		SAC

CONFIDENTIAL

205667

No.	Population	IDSL / TST ID / Example Shell	Title	Programming Notes	Deliverable [Priority]
Safety : Tables					
Adverse Events of Special Interest					
11.20	All Subjects	AE1	Summary of On-Treatment Adverse Events Reported by the Investigator as Meeting the Criteria for Anaphylaxis		SAC
11.21	All Subjects	TAB_S1	Summary Profile of On-Treatment Adverse Events Reported by the Investigator as Meeting the Criteria for Anaphylaxis		SAC
11.22	All Subjects	AE1	Summary of On-Treatment Adverse Events Defined by the Investigator as Systemic Reactions - Allergic (Type I Hypersensitivity) and Other Systemic		SAC
11.23	All Subjects	TAB_S1	Summary Profile of On-Treatment Adverse Events Defined by the Investigator as Systemic Reactions - Allergic (Type I Hypersensitivity) and Other Systemic		SAC
11.24	All Subjects	AE1	Summary of On-Treatment Adverse Events Defined by the Investigator as Systemic Reactions - Allergic (Type I Hypersensitivity)		SAC
11.25	All Subjects	TAB_S1	Summary Profile of On-Treatment Adverse Events Defined by the Investigator as Systemic Reactions - Allergic (Type I Hypersensitivity)		SAC
11.26	All Subjects	AE1	Summary of On-Treatment Adverse Events Defined by the Investigator as Systemic Reactions – Other Systemic		SAC
11.27	All Subjects	TAB_S1	Summary Profile of On-Treatment Adverse Events Defined by the Investigator as Systemic Reactions - Other Systemic		SAC
11.28	All Subjects	AE1	Summary of On-Treatment Adverse Events Defined by the Investigator as Local Injection Site Reactions		SAC

CONFIDENTIAL

205667

No.	Population	IDSL / TST ID / Example Shell	Title	Programming Notes	Deliverable [Priority]
Safety : Tables					
11.29	All Subjects	TAB_S1	Summary Profile of On-Treatment Adverse Events Defined by the Investigator as Local Injection Site Reactions		SAC
11.30	All Subjects	AE1	Summary of On-Treatment Adverse Events Categorised as Serious Cardiac, Vascular and Thromboembolic Events		SAC
11.31	All Subjects	TAB_S1	Summary Profile of On-Treatment Adverse Events Categorised as Serious Cardiac, Vascular and Thromboembolic Events		SAC
11.32	All Subjects	AE1	Summary of On-Treatment Adverse Events Categorised as Serious Ischemic Events		SAC
11.33	All Subjects	TAB_S1	Summary Profile of On-Treatment Adverse Events Categorised as Serious Ischemic Events		SAC
11.34	All Subjects	AE1	Summary of On-Treatment Adverse Events Categorised as Malignancies		SAC
11.35	All Subjects	TAB_S1	Summary Profile of On-Treatment Adverse Events Categorised as Malignancies		SAC
11.36	All Subjects	AE1	Summary of On-Treatment Adverse Events Categorised as Opportunistic Infections		SAC
11.37	All Subjects	TAB_S1	Summary Profile of On-Treatment Adverse Events Categorised as Opportunistic Infections		SAC
Laboratory - Haematology					
11.38	All Subjects	LB1	Summary of Haematology Changes from Baseline by Visit	Include baseline values	SAC
11.39	All Subjects	LB3	Summary of Haematology Shifts from Baseline Relative to Normal Range by Visit		SAC

CONFIDENTIAL

205667

No.	Population	IDSL / TST ID / Example Shell	Title	Programming Notes	Deliverable [Priority]
Safety : Tables					
11.40	All Subjects	LB3	Summary of Haematology Shifts from Baseline Relative to PCI Criteria by Visit		SAC
Laboratory – Clinical Chemistry					
11.41	All Subjects	LB1	Summary of Clinical Chemistry Changes from Baseline by Visit	Include baseline values	SAC
11.42	All Subjects	LB3	Summary of Clinical Chemistry Shifts from Baseline Relative to Normal Range by Visit		SAC
11.43	All Subjects	LB3	Summary of Clinical Chemistry Shifts from Baseline Relative to PCI Criteria by Visit		SAC
ECG					
11.43	All Subjects	EG1	Summary of ECG Findings by Visit		SAC
11.45	All Subjects	EG2	Summary of ECG Values by Visit		SAC
11.46	All Subjects	EG2	Summary of Change from Baseline in ECG Values by Visit	Include baseline values	SAC
Vital Signs					
11.47	All Subjects	VS1	Summary of Vital Signs by Visit		SAC
11.48	All Subjects	VS1	Summary of Change from Baseline in Vital Signs by Visit	Include baseline values	SAC
Injection Pain Assessments					
11.49	All Subjects	TAB_S3	Summary of Injection Pain – VAS Scores (mm)	By Visit and time point post-injection (injection, 1 hr post, 24 hrs post)	SAC
11.50	All Subjects	TAB_S4	Summary of Injection Pain – Categorical Pain Assessment	By Visit and time point post-injection (injection, 1 hr post, 24 hrs post)	SAC

